## 5.5. Dose Justification

Not applicable.

## 6. STUDY POPULATION

Prospective approval of protocol deviations to recruitment and enrolment criteria, also known as protocol waivers or exemptions, is not permitted.

Participants will be eligible for inclusion in the main cohort only if all inclusion criteria apply and none of the exclusion criteria apply.

Eligible participants in the main cohort from selected Type A hospitals, consented with willingness to use electronic devices for daily patient-reported outcomes collection (e.g. logpads), attend more frequent visits and receive additional assessments will be recruited to the Biomarker and Digital sub-cohort.

It is planned to enrol approximately 1,700 COPD subjects in the study, approximately 180 controls with chronic bronchitis, and approximately 120 never smoker healthy controls.

COPD subjects will fall into the GOLD categories I - IV. It is intended to recruit the COPD subjects in the following manner: 700 GOLD I, 700 GOLD II, 200 GOLD III and 100 GOLD IV.

All patient population sizes are approximate and subject to feasibility.

### 6.1. Inclusion Criteria

#### COPD Participants

A COPD subject will be eligible for inclusion in this study only if all the following criteria apply:

1. Male or female participants, aged 40-80 years inclusive.

A female is eligible to enter and participate in the study if she is of non-child bearing potential.

2. A baseline (post-bronchodilator) FEV1/FVC ratio  $<0.70$

3. Clinically stable and has no exacerbations for at least 1 month prior to recruitment.  
All courses of oral corticosteroids or antibiotics must be completed at least 2 weeks before study start.

4. Ever smoker (with a lifetime exposure of  $\geq 1$  pack-year) or never smoker (with a lifetime exposure of  $<1$  pack-year)

5. A signed and dated written informed consent is obtained prior to participation

6. Additional criteria for sub-cohort COPD participants to be recruited:

- Only include participants aged 50-80 years (inclusive)
- $BMI < 35 \text{ kg/m}^2$

- Only include ever smoker with a lifetime exposure of  $\geq 10$  pack-year or never smoker with a lifetime exposure of  $<1$  pack-year
- About 150 COPD participants with a history of at least 1 exacerbation event(s) within the past 2 years at the entry of the study
- About 60 COPD participants without inhaler maintenance treatment history for at least 12 months prior to the entry of the study (including inhaled corticosteroids, inhaled long-acting antimuscarinics, and inhaled long-acting beta2-agonists).

## Chronic Bronchitis Participants

A chronic bronchitis participant will be eligible for inclusion in this study only if all of the following criteria apply:

1. Male or female participants, aged 40-80 years inclusive, who are free from significant disease as determined by history, physical examination and screening investigations.  
A female is eligible to enter and participate in the study if she is of non-child bearing potential.
2. Baseline post-bronchodilator FEV1/FVC ratio  $\geq 0.70$ .
3. Chronic bronchitis is defined as at least 3 months of cough and phlegm in a year in the past 2 years.

The definition of chronic bronchitis is used for recruiting subjects to Chronic Bronchitis group. This would be identified by asking two questions such as: "How many MONTHS in the past 12 months have you had bronchitis or chronic coughing with phlegm or sputum from the chest?" AND "For how many years have you had bronchitis or chronic coughing with phlegm or sputum from the chest?" with at least 3 months in past year and for at least past 2 years representing a minimum qualifying criteria.

4. Clinically stable and has no exacerbations for at least 1 month prior to recruitment.
5. Ever smoker (with a lifetime exposure of  $\geq 1$  pack-year) or never smoker (with a lifetime exposure of  $<1$  pack-year)
6. A signed and dated written informed consent is obtained prior to participation.
7. Additional criteria for sub-cohort Chronic Bronchitis participants to be recruited:
  - Only include participants aged 50-80 years (inclusive)
  - BMI  $<35$  kg/m^2
  - Only include ever smoker with a lifetime exposure of  $\geq 10$  pack-year or never smoker with a lifetime exposure of  $<1$  pack-year

## Healthy Participants

1. Male or female participants, aged 40-80 years inclusive, who are free from significant disease as determined by history, physical examination and screening investigations.  
A female is eligible to enter and participate in the study if she is of non-child bearing potential.
2. Baseline post-bronchodilator FEV1/FVC ratio  $\geq 0.70$
3. A CAT score  $<10$
4. Never smoker with a lifetime exposure of  $<1$  pack-year. Passive smoker is not eligible
5. A signed and dated written informed consent is obtained prior to participation.
6. Additional criteria for sub-cohort Healthy participants to be recruited:
  - Only include participants aged 50-80 years (inclusive)
  - BMI  $<35$  kg/m^2

## 6.2. Exclusion Criteria

### COPD Participants

A COPD participant will not be eligible for inclusion in this study if any of the following criteria applied:

1. In the opinion of the investigator, there was a current primary diagnosis of asthma (patients with a primary diagnosis of COPD but who also had asthma could be included).
2. Known respiratory disorders, or disorders identified at screening/visit 1 (including identification on the first CT scan), other than COPD (e.g. COVID-19, lung cancer, sarcoidosis, active tuberculosis, lung fibrosis, cystic fibrosis) that may significantly impact clinical assessments according to investigator judgement
3. Having undergone lung surgery (e.g. lung reduction, lung transplant)
4. Known history of significant inflammatory disease, other than COPD (e.g. rheumatoid arthritis and Lupus)
5. Serious, uncontrolled disease (including serious psychological disorders) likely to interfere with the study or impact on subject safety
6. Diagnosis of cancer: included current and within the last 5 years (patients in remission for  $\geq 5$  years could be included).
7. Participants who were concurrently participating in any clinical studies where investigational drugs were tested within 4 weeks prior to Visit 1 (baseline), or who were scheduled to start any during the study period or enrolled in a study where there is significant radiation exposure (e.g. CT scans).

8. Unable or unwilling to use required digital devices, e.g. wrist band, digital diary (sub-cohort only)
9. Have, in the opinion of the investigator, evidence of alcohol or drug abuse
10. Have received a blood transfusion in the 4 weeks prior to study start
11. Is on long term oral corticosteroids (long term is considered use for more than 3 consecutive months)
12. Unable to walk
13. Unable to read and understand Chinese

### **Chronic Bronchitis Participants**

A chronic bronchitis participant will not be eligible for inclusion in this study if any of the following criteria applied:

1. Known respiratory disorders, or disorders identified at screening/visit 1 (including identification on the first CT scan), (e.g.: COVID-19, COPD, current asthma, lung cancer, sarcoidosis, active tuberculosis, lung fibrosis, cystic fibrosis) that may significantly impact clinical assessments according to investigator judgement
2. Post-bronchodilator FVC<80% Predicted normal
3. Having undergone lung surgery (e.g. lung reduction, lung transplant)
4. Known history of significant inflammatory disease, other than COPD (e.g. rheumatoid arthritis and Lupus)
5. Serious, uncontrolled disease (including serious psychological disorders) likely to interfere with the study or impact on subject safety
6. Diagnosis of cancer – included current and within the last 5 years (patients in remission for  $\geq$  5 years could be included).
7. Participants who were concurrently participating in any clinical studies where investigational drugs were tested within 4 weeks prior to Visit 1 (baseline), or who were scheduled to start any during the study period, or enrolled in a study where there is significant radiation exposure (e.g. CT scans).
8. Unable or unwilling to use required digital devices, e.g. wrist band, digital diary (sub-cohort only)
9. Have, in the opinion of the investigator, evidence of alcohol or drug abuse
10. Have received a blood transfusion in the 4 weeks prior to study start
11. Is on long term oral corticosteroids (long term is considered use for more than 3 consecutive months)
12. Unable to walk
13. Unable to read and understand Chinese

## Healthy Participants

A healthy participant will not be eligible for inclusion in this study if any of the following criteria applied:

1. Known respiratory disorders or disorders identified at screening/visit 1 (including identification on the first CT scan) (e.g. COVID-19, COPD, current asthma, lung cancer, sarcoidosis, active tuberculosis, lung fibrosis, cystic fibrosis) that may significantly impact clinical assessments according to investigator judgement
2. Post-bronchodilator FVC<80% Predicted normal
3. Having undergone lung surgery (e.g. lung reduction, lung transplant)
4. Known history of significant inflammatory disease, other than COPD (e.g. rheumatoid arthritis and Lupus)
5. Serious, uncontrolled disease (including serious psychological disorders) likely to interfere with the study or impact on subject safety
6. Diagnosis of cancer – included current and within the last 5 years (patients in remission for  $\geq 5$  years could be included).
7. Participants who were concurrently participating in any clinical studies where investigational drugs were tested within 4 weeks prior to Visit 1 (baseline), or who were scheduled to start any during the study period, or enrolled in a study where there is significant radiation exposure (e.g. CT scans).
8. Unable or unwilling to use required digital devices, e.g. wrist band, digital diary (sub-cohort only)
9. Have, in the opinion of the investigator, evidence of alcohol or drug abuse
10. Have received a blood transfusion in the 4 weeks prior to study start
11. Is on long term oral corticosteroids (long term is considered use for more than 3 consecutive months)
12. Unable to walk
13. Unable to read and understand Chinese

### 6.3. Lifestyle Restrictions

No lifestyle restrictions are required.

### 6.4. Screen Failures

Screen failures are defined as participants who consent to participate in the study but are not subsequently entered in the study. A minimal set of screen failure information is required to ensure transparent reporting of screen failure participants. Minimal information includes demography, screen failure details, eligibility criteria.

Individuals who do not meet the criteria for participation in this study (screen failure) may not be rescreened. Only in certain special cases, re-screening of participants will be

allowed. Investigator will be asked to provide detailed information. Special cases will be discussed at the EST (empowered study team) meeting. After permission from the medical monitor of this study is granted, the participants can only be re-screened once.

## **7. TREATMENTS**

This cohort study will not provide or recommend any treatment. Patients' diagnosis and treatment will be left to their physicians' judgement and routine practice. This section is not applicable.

### **7.1. Treatments Administered**

Not applicable.

### **7.2. Dose Modification**

Not applicable

### **7.3. Method of Treatment Assignment**

Not applicable

### **7.4. Blinding**

Not applicable

### **7.5. Preparation/Handling/Storage/Accountability**

Not applicable

### **7.6. Treatment Compliance**

Not applicable

### **7.7. Concomitant Therapy**

Not applicable

### **7.8. Treatment after the End of the Study**

Not applicable

## **8. DISCONTINUATION CRITERIA**

### **8.1. Discontinuation of Study Treatment**

Not applicable. This cohort study will not provide or recommend any treatment. Patients' diagnosis and treatment will be left to their physicians' judgement and routine practice.

### **8.2. Withdrawal from the Study**

- A participant may withdraw from the study at any time at his/her own request, or may be withdrawn at any time at the discretion of the investigator for safety, behavioural, compliance or administrative reasons.
- A subject will be considered withdrawn from the study if he/she joins any clinical studies where investigational drugs are tested.
- If the participant withdraws consent for disclosure of future information, the sponsor may retain and continue to use any data collected before such a withdrawal of consent. If a participant withdraws consent for disclosure, the site may use any publicly information to determine vital status at the end of the study and this information would be included in the final analyses.
- If a participant withdraws from the study, he/she may request destruction of any samples taken and not tested, and the investigator must document this in the site study records.

### **8.3. Lost to Follow Up**

A participant will be considered lost to follow-up if he or she is unreachable and fails to come back for both Visit 3 and 4.

## 9. STUDY ASSESSMENTS AND PROCEDURES

Study procedures and their timing are summarized in schedule of activities ([Table 1](#))

Protocol waivers or exemptions are not allowed.

Immediate safety concerns should be discussed with the sponsor immediately upon occurrence or awareness to determine if the participant should continue or discontinue the study.

Site staff will make every effort to work with participants to collect all study assessments.

All screening evaluations must be completed and reviewed to confirm that potential participants meet all eligibility criteria. The investigator will maintain a screening log to record details of all participants screened and to confirm eligibility or record reasons for screening failure, as applicable.

Procedures conducted as part of the participant's routine clinical management (eg, spirometry) and obtained before signing of informed consent form (ICF) may be utilized for screening or baseline purposes provided the procedure met the protocol-specified criteria and was performed within the time frame defined in the SoA.

### 9.1. Baseline data collection

A specifically designed baseline survey will be used to collect the following information at baseline from all participants, including:

Informed consent

Inclusion/exclusion criteria assessment

Socio-demographics

- Age
- Race/ethnicity
- Gender
- Education
- Economic status
- Occupation
- Insurance information (basic, commercial)

Health and lifestyle information

- Height, weight, body mass index (BMI)
- Blood pressure, heart rate
- Smoking status: Never smokers are defined as those with a lifetime exposure of <1 package/year in their life (excluding passive smoker). Ever smokers (current or former) are defined as those with a lifetime exposure of ≥10 package/year.

Former smokers are those who have stopped smoking for at least 6 months.

Current smokers are those who are currently smoking. Passive smokers are

defined as those with the presence of smokers living in the same household, or co-workers smoking nearby while indoors

- Smoking history including Pack-years of smoking: Number of pack years = (number of cigarettes per day / 20) x number of years smoked, e.g., 10 pack-years means 20 cigarettes per day for 10 years, or 10 cigarettes per day for 20 years)
- Biomass exposure: refer to the biomass exposure questionnaire
- Occupational exposures: Whether had the participant worked in occupations known or suspected to be associated with the risk of COPD  $\geq 6$  months, e.g. organic/inorganic dust, irritant gases, fumes, or vapors chef, traffic police Toxic and harmful jobs (eg.in pollution factory or chemical work, etc)

COPD Medical history (for COPD participants only)

- Disease duration
- Treatment history (e.g. the time of initiating maintenance treatment, current treatment)
- Number of exacerbations in the previous 12 months and 24 months
- Number of moderate and severe exacerbations in the previous 12 months and 24 months and their management with oral corticosteroids and/or antibiotics and/or hospitalization
- Family history of COPD or other respiratory diseases

Lower respiratory infections including chest colds (for chronic bronchitis patients only)

Medical history (including previous asthma history)

Current co-morbid conditions and childhood respiratory disease

Concomitant medications: Respiratory medications, antibiotics, oral steroids, anti-diabetic, anti-hypertension gastroesophageal reflux disease (GERD) therapy, cardiovascular disease therapy and whether taking traditional Chinese medicines

Patient reported outcomes: CAT, SGRQ-C and mMRC, CAPTURE

Spirometry (pre- and post-bronchodilator)

- FEV1
- Forced vital capacity (FVC) & Percent Predicted FVC and FEV1/FVC ratio & Percent Predicted FEV1/FVC
- Forced expiratory volume in 6 seconds (FEV6)
- Forced expiratory flow between 25% and 75% of vital capacity (FEF 25-75) & Percent Predicted FEF 25-75, Forced Expiratory Flow 25% (FEF25), Forced Expiratory Flow 50% (FEF50) and Forced Expiratory Flow 75% (FEF75)
- Peak Expiratory Flow (PEF) & Percent Predicted PEF, time to Peak Expiratory Flow (tPEF) and Maximal Mid-Expiratory Flow (MMEF)
- Forced Expiratory Time (FET) and Volume back extrapolation (VEXT)

- FEV1 percent of predicted and reversibility test
  - Reversibility will be assessed at Visit 1 (baseline) by measurement of FEV1 before and 10 to 30 minutes after administration of a short-acting bronchodilator (e.g. 400µg β2-agonist or up to 160µg anticholinergic). Prior to testing, the patients should not have taken inhaled short-acting bronchodilators in the previous six hours, long-acting bronchodilator in the previous 12 hours or sustained-release theophylline in the previous 24 hours.
  - Reversibility will be calculated as follows: % Reversibility =  
$$\frac{\text{Highest post - bronchodilator FEV}_1 - \text{Highest pre - bronchodilator FEV}_1}{\text{Highest pre - bronchodilator FEV}_1} \times 100$$

Collection of blood samples for protocol defined analysis (plasma fibrinogen and hsCRP, total and differential blood cell count)

In addition, the following assessments will be conducted among the Biomarker & Digital sub-cohort participants only:

Blood biomarkers (including serum sRAGE, CC16, IP-10, HbA1c)

Sputum sample collection for protocol defined analyses (microbiome through molecular methods, cytology)

Lung HRCT

Issue and training in use of electronic diary: EXACT questionnaire (start after clinic visit at baseline)

Digital steps (start after clinic visit at baseline)

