| Section 6.1. Inclusion Criteria-COPD, Chronic Bronchitis  | Reduced the pack-year limit for all ever smokers in the main cohort from 10 to 1   | Allow the recruitment of ever smokers with 1-10 pack-year in the main cohort. Pack years smoking is very closely related to age. The typical patient with established moderate-severe COPD who is for example 65 years old will have smoked for 20 years more than a 45 year old.   |
| Section 6.1. Inclusion Criteria-COPD participants   | Edited “A baseline (post-bronchodilator) FEV1/FVC ratio <70%” to “A baseline (post-bronchodilator) FEV1/FVC ratio <0.70”

Removed the requirement for the severity of historical exacerbation event (moderate or severe) in the additional criteria for sub-cohort | Use a fraction to 2 decimal places rather than a percentage of a whole number to make this inclusion criterion more precise and keep consistent with other COPD studies. This becomes especially important for patients with mild airflow limitation – who are an important subgroup in COMPASS

Ensure consistency across the protocol |
| Section 6.1. Inclusion Criteria-Chronic Bronchitis and healthy participants   | Edited “Baseline post-bronchodilator FEV1/FVC ratio >70%” to “Baseline post-bronchodilator FEV1/FVC ratio ≥0.70”   | To involve in participants whose Baseline post-bronchodilator FEV1/FVC ratio is greater than or equal to 0.70   |
| Section 6.2. Exclusion Criteria-COPD, Chronic Bronchitis and healthy participants (common to all the group of participants) | Specified that COVID-19 should be excluded in each group

Removed “Mandarin” in the No. 13 exclusion criterion related to read and understand Chinese  | Provide specified information

To make it clear. There are lots of local languages in China. Mandarin is the most widely used official language. To allow the participants to participate in the study who can speak other local languages except Mandarin  |

|  |  |   |
|--|--|---|
| Section 6.2.
Exclusion
Criteria-Chronic
Bronchitis and
healthy
participants | Edited “FVC<80% Predicted”
to “Post-bronchodilator
FVC<80% Predicted normal”   | According to GOLD and
ATS/ERS criteria, clarify the
requirement of post
bronchodilator FVC <80%
Predicted normal.   |

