## 5.4. Scientific Rationale for Study Design

To reflect the real-world management and patient outcomes of COPD in China, a non-drug interventional study design was chosen. Patient diagnosis and treatment will be left to their physicians' judgement and routine practice. This study will not provide or recommend any treatment. By capturing the prospective and longitudinal patient-level data in a real-world clinical setting, the study will fulfil the needs to understand the phenotypes and their disease progression, and current disease management more comprehensively and in depth. Study results will inform clinical practice and may improve patient outcomes.

This study will use COPD and non-COPD cohorts to provide cross-sectional and longitudinal data on multiple clinical, radiological and biological evaluations. Study participants will mostly represent mild to moderate airflow limitation grades of COPD and symptomatic non-COPD (i.e. chronic bronchitis) populations, whose disease progression is not well understood in China.

Air pollution and increased biomass exposure are likely to be key contributors to the development of COPD in China. Previous nation-wide studies showed a large proportion of COPD patients (20-40%) in China are never smokers. Kurmi et al. reported that 5.4% of never smokers had airflow obstruction (AFO) among Kadoorie cohort [[Kurmi, 2014](#)]. The prevalence of COPD was estimated to be 5.2% among never smokers in Zhong et al [[Zhong, 2007](#)]. This suggested that factors other than smoking (e.g. biomass, occupational exposure, and air pollution) may also play an important role in COPD progression. However, there is a lack of data on phenotypes and disease progression in never smokers with COPD. Differing from the Western cohorts in which participants were required to have at least 10-pack year smoking history, never smokers with diagnoses of COPD or chronic bronchitis (with respiratory symptoms who don't meet the spirometric criteria of COPD) are also recruited. In addition, air pollution data will be collected retrospectively to explore the association between air pollution and COPD natural history.

Healthy subjects who are never smokers and without a diagnosis of respiratory condition and other significant diseases will also be recruited to this study as controls, e.g. providing data on baseline natural lung function decline and lung structural damage in a general population.

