### 5.5.2. Examination of Subgroups

Subgroup definitions in main cohort were listed as follows,

- Age (<65 years, >65 at baseline)
- Site (Type A and Type B Hospital)
- Smoking status (Baseline ever/never smoker)
- History of exacerbation in the preceding years (Any exacerbation/No exacerbation)
- Inhaled treatment naïve (Yes/No)
- Childhood respiratory disease (Yes/No)
- Biomass fuel exposure (Yes/No)
- Presence of chronic bronchitis (Yes/No)

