#### **Model Results Presentation**

- Baseline FEV1 or FVC will be provided with n (number of subjects included in the analysis) and mean(SD).
- The adjusted rate of change (decline), differences in different type of subjects compared with Health Control, nominal p-values and 95% confidence limits will be provided.

Subgroup analysis of rate of change in FEV1 will be analysed using the same random coefficients model. Number of subjects included in the model, baseline value, adjusted rate of change and difference compared with healthy control will be provided without p-value.

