### 17.5.2. Study Population

Demographics	
Age	
• Age will be calculated based on the Visit 1.	
• Birth date will be imputed as follows:	
• Any subject with a missing day will have this imputed as day '15'.	
• Any subject with a missing date and month will have this imputed as '30JUN'.	
• Birth date will be presented in listings as 'YYYY'.	
Age categories are based on at screening and are defined as:	
• <65 years	
• ≥65 years	

Subject disposition	
Discontinuation from Study Treatment	
Not Applicable.	

Subject disposition
Discontinuation from Study Treatment
Discontinuation from Study

Censoring will be performed as follows:
 
 
• For subject that withdraws consent for disclosure of future information, any data collected prior to withdrawal will be retained and reported.
 
• For subject that withdraws consent for disclosure, the site may use any publicly information to determine vital status at the end of the study and this information would be included in the final analyses.
 
• If a subject withdraws from the study, he/she may request destruction of any samples taken and not tested, such request will be documented in study records.
 
• Subject that is unreachable and fails to come back for both Visit 3 and Visit 4 will be considered lost to follow-up. Data collected prior to missed visits will be retained and reported.
 

Smoking status

 
• Smoking status: Never smokers are defined as those with a lifetime exposure of <1 package/year in their life (excluding passive smoker). Ever smokers (current or former) are defined as those with a lifetime exposure of <math>\geq 10</math> package/year. Former smokers are those who have stopped smoking for at least 6 months. Current smokers are those who are currently smoking. Passive smokers are defined as those with the presence of smokers living in the same household, or co-workers smoking nearby while indoors
 
• Smoking status will be reassessed at each scheduled clinic visit evaluated by participants' self-report (e.g. never smoker, current smoker, former smoker).
 
• Smoking history including Pack-years of smoking: Number of pack years (number of cigarettes per day / 20) x number of years smoked, e.g., 10 packyears means 20 cigarettes per day for 10 years, or 10 cigarettes per day for 20 years)
 

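### SAP 17.5.2 and protocol 9.1 start ever smokers at 10 pack-years while main-cohort eligibility starts them at 1, so participants with 1 to <10 pack-years have no level in the ever/never FEV1-slope subgroup

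*Protocol*

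**What the plan says.** **Analysis definition.** Protocol 9.1 defines never smokers as below 1 pack-year, with passive smokers excluded in brackets, and then states: "Ever smokers (current or former) are defined as those with a lifetime exposure of ≥10 package/year". SAP 17.5.2 carries the same two definitions; its second sentence opens "Ever smokers (current or former) are defined as those with a lifetime exposure of" and gives 10 as the limit. Current and former smokers are then described without a pack-year limit of their own.

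**Eligibility.** Protocol 6.1, COPD criterion 4, reads "Ever smoker (with a lifetime exposure of" at least 1 pack-year, or never smoker below 1. Chronic bronchitis criterion 5 is the same. The limit of 10 survives in 6.1 only among the additional sub-cohort criteria for these two groups: "Only include ever smoker with a lifetime exposure of" at least 10 pack-years, or never smoker below 1. Healthy controls must be never smokers. The Amendment 2 table gives the purpose of the lower main-cohort limit: "Allow the recruitment of ever smokers with 1-10 pack-year in the main cohort".

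**Use.** SAP 5.5.2 lists the subgroup factor "Smoking status (Baseline ever/never smoker". SAP 8.1 adds: "Subgroup analysis of rate of change in FEV1 will be analysed using the same random coefficients model", with results shown without p-values. Smoking status is also a covariate in the negative binomial model (SAP 7.1) and in the MMRM and random coefficients models (SAP 8.1), and a subgroup for treatment patterns (SAP 14.1). None of these four places states its levels.

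**The concern.** SAP 17.5.2 is the section a programmer would use to derive the variable. It leaves a gap exactly where Amendment 2 deliberately opened recruitment. Followed literally, it leaves the lighter smokers out of the ever/never display of FEV1 slope, and ever smoker then means only those with 10 pack-years or more. If it is not followed, someone has to override the SAP's own rule, and the SAP records no such decision. The contrast matters to the design: protocol 5.4 says "there is a lack of data on phenotypes and disease progression in never smokers with COPD", and this subgroup is where the slopes of never and ever smokers are shown.

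**Working it through.** No published figure needs reproducing; the check is whether each pack-year value receives exactly one level under each rule. I read the unit in protocol 9.1 and SAP 17.5.2 as pack-years, because both sections go on to give the pack-year formula.

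| Lifetime exposure (pack-years) | Protocol 6.1, main cohort | Protocol 9.1 / SAP 17.5.2 | SAP 17.5.2 with the threshold at 1 |
|---|---|---|---|
| 0, 0.5, 0.99 | never | never | never |
| 1, 2, 5, 9.9 | ever | neither | ever |
| 10, 20 | ever | ever | ever |

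The rules agree below 1 and from 10 upwards. They differ only from 1 to <10, where the analysis rule has no level. The never row is the same in every column.

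**Who can be in the gap under current criteria.** Healthy controls cannot, being never smokers. Sub-cohort COPD and chronic bronchitis participants cannot, since they must be below 1 or at least 10. Using the planned sizes in protocol 5.2:

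- COPD plus chronic bronchitis: 1,700 + 180 = 1,880.
- Of these, in the sub-cohort: 100 chronic bronchitis + 100 GOLD I + 100 GOLD II + 50 GOLD III = 350.
- Remaining: 1,880 − 350 = 1,530, which is 1,530 / 2,000 = 76.5% of the planned total.

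The 1,530 includes never smokers (up to 30% of each group) and everyone with 10 or more pack-years, so it shows where affected people could be, not how many there are. The documents give no pack-year distribution. For scale only, each 1% of that pool is 0.01 × 1,530 = 15.3, or about 15 people.

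**Choice or carry-over?** The SAP states that it is based on protocol Amendment 2, and its list of departures from the protocol (SAP 2.1) does not mention smoking. SAP Appendices 2 and 3 also still show visit windows of +3 and ±28 days, where the current protocol has +7 and ±30. This suggests a definition left unrevised, but that is an inference.

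**The case against.** **Protocol 6.1 already settles the matter.** It divides participants completely at 1 pack-year and labels those with 1 to <10 as ever smokers. This stands as far as it goes: these participants can be classified, and the intended answer is clear. But the SAP's own derivation says otherwise, and nothing in it gives 6.1 precedence.

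**The models may be untouched.** Smoking status at follow-up is self-reported as never, current or former, and the last two have no pack-year limit of their own. The appended earlier RAP codes the variable that way in its logistic model for exacerbations over 18 months. This also largely stands. A reader might infer that participants with 1 to <10 pack-years would be set to missing and drop out of the exacerbation, MMRM and slope models. The documents do not support that: the covariate's levels are not stated, and a never/current/former coding could place everyone. What remains is ambiguity, because the sentence that sets the limit of 10 names current and former smokers together.

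**The never-smoker question is not affected.** Correct on the pack-year bound. A reader might infer from protocol 5.4 that evidence on never smokers is compromised, but their limit is below 1 under both rules. Only the group beside them changes.

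**The sub-cohort may not be wholly clear.** The Amendment 1 table records that smoking was at first defined by a count of 100 cigarettes, and the documents do not say whether anyone was enrolled under that rule. The sub-cohort is therefore unaffected under current criteria, not in every possible case.

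**Conclusion.** The conflict is real and is in current text. As written, SAP 17.5.2 gives main-cohort participants with 1 to <10 pack-years no level in the ever/never subgroup for FEV1 slope, and leaves their level unclear in the other four uses of smoking status. The consequence is small to moderate. It concerns the make-up of the ever group in a descriptive study, in a subgroup reported without p-values. The number affected is unknown and may be small, and the documents do not show in which direction the ever-smoker slope would move. The conclusion assumes that the unit in both definitions is pack-years and that SAP 17.5.2 governs the derived variable.

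**What to change.** In SAP 17.5.2, change the ever-smoker threshold from 10 to 1 pack-year to match protocol 6.1, and keep 10 only as a sub-cohort eligibility rule. Every participant with 1 pack-year or more is then an ever smoker, so the ambiguity in the covariates closes as well.

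Leave the never-smoker bound at <1, and do not drop the passive-smoker qualifier in passing. State which of two things it means: that passive exposure does not count towards pack-years, or that passive smokers are removed from the never group. The second reading would change the never group among COPD and chronic bronchitis participants, for whom passive smoking is no bar to entry; protocol 6.1 bars it only for healthy controls.

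Align protocol 9.1 at the next amendment. Protocol amendments need ethics approval (protocol Appendix 2), and the analysis need not wait for one. The cost is a few lines in the SAP: pack-years are already collected at baseline, and no sample-size figure changes.
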